- Mild: The AE is noticeable to the subject but does not interfere with routine activity and does not require medical treatment
- Moderate: The AE interferes with routine activity but responds to symptomatic therapy or rest. Usually requires medical treatment.
- **Severe:** The AE requires removal of the implant. The subject is at risk of death or loss of a limb.

E. Recording and Reporting Adverse Events

SAEs must be reported to MPO as soon as possible but no later than **10 calendar days** of the Investigator (or site personnel) becoming aware. This includes:

- All primary THA procedure related SAEs from time of THA implantation to the enrollment, and through subjects' study completion or withdrawal.
- If unable to provide as instructed, the Investigator (or site personnel) will notify Clinical Data Management at MPO (contact information listed in the Study Binder).

If a follow up report is required for a unresolved SAE it must be reported as soon as possible but no later than **10 calendar days** of the Investigator (or site personnel) becoming aware of additional information.

ADEs, UADEs , SADEs and USADEs must be reported to MPO as soon as possible but no later than **10 calendar days** of the Investigator (or site personnel) becoming aware. This includes:

- All UADEs, SADEs, and USADEs from the time of THA implantation through subjects' study completion or withdrawal.
- If unable to provide as instructed, the Investigator will notify Clinical Data Management at MPO (contact information listed in the Study Binder).

If a follow up report is required for unresolved UADEs, SADEs or USADEs it must be reported as soon as possible but no later than **10 calendar days** of the Investigator (or site personnel) becoming aware of additional information.

Upon MPO's request, the Investigator must supply any additional information related to the safety reporting of any event.

F. Adverse Event Status Update

The Investigator will follow subjects who experience an Adverse Event until it is resolved or the Investigator assesses them as chronic or stable or until the subject's participation in the study ends. Prior to completion of the study, the Investigator will document the resolution date. If surgical intervention is required to treat the AE, the Investigator will document the details of the intervention.

Any surgical interventions will be classified as follows:

- Reoperation with no revision: Reoperation without revision would include procedures such as irrigation and debridement to treat infection
- Revision of one or more components: Revision is a procedure that adjusts or in any way modifies the original component configuration
- **Removed:** Removal is a procedure that removes the original components
- Non Sponsor Device: Reoperation that modifies, adjusts, removes or adds nonsponsor components.
- Other: Any other kind of surgery that does not revise or remove the components

Clinical Data Management should be notified prior to performing a surgical intervention that removes any of the implanted components (contact information can be found in the Study Binder). MPO will provide instructions on the appropriate methods for returning explanted devices to MPO. Any MPO component removed during a surgical intervention will be sent back to MPO for investigation.

G. Anticipated Adverse Events

Anticipated device and THA procedure related adverse events include [4]:

- Osteolysis (progressive bone resorption);
- Particulates leading to increased wear rates necessitating early revision;
- Allergic reactions to materials; metal sensitivity that may lead to histological reactions, pseudotumor, and aseptic lymphocytic vasculitis-associated lesions (ALVAL);
- Delayed wound healing; deep wound infection (early or late) which may necessitate removal of the prosthesis; on rare occasions, arthrodesis of the involved joint or amputation of the limb may be required;
- A sudden drop in blood pressure intra-operatively due to the use of bone cement;
- Damage to blood vessels or hematoma;
- Temporary or permanent nerve damage, peripheral neuropathies, and subclinical nerve damage as possible result of surgical trauma resulting in pain or numbness of the affected limb;
- Cardiovascular disorders including venous thrombosis, pulmonary embolism, or myocardial infarction;
- Fatigue fracture of the prosthetic component can occur as a result of trauma, strenuous activity, improper alignment, incomplete implant seating, duration of service, loss of fixation, non-union, or excessive weight;
- Dislocation, migration, and/or subluxation of prosthetic components from improper positioning, trauma, loss of fixation, and/or muscle and fibrous tissue laxity;

 Periarticular calcification or ossification, with or without impediment to joint mobility;

- Trochanteric non-union due to inadequate reattachment and or early weight bearing;
- Trochanteric avulsion as a result of excess muscular tension, early weight bearing, or inadvertent intraoperative weakening;
- Traumatic arthrosis of the knee from intraoperative positioning of the extremity;
- Inadequate range of motion due to improper selection or positioning of components, by femoral impingement, and periarticular calcification;
- Femoral or acetabular perforation or fracture; femoral fracture while seating the device; femoral fracture by trauma or excessive loading, particularly in the presence of poor bone stock;
- Undesirable shortening or lengthening of the limb;
- Aggravated problems of the affected limb or contralateral extremity by leg length discrepancy, excess femoral medialization, or muscle deficiency;
- Pain.

XV. AMENDMENTS TO CLINICAL PROTOCOL

Amendments cannot be made to the clinical protocol without the written consent of MPO. Since this is an FDA-ordered study, amendments to the protocol will only be enacted after receiving approval from FDA. Additionally, amendments to the protocol must be approved by the Institutional Review Board/Ethics Committee (IRB/EC) prior to their implementation. Statistical Analysis Plan will be also updated according to the protocol amendments as necessary.

XVI. DEVIATIONS FROM CLINICAL PROTOCOL

Investigators will not deviate from the clinical protocol except to deliver emergency care or to eliminate an immediate hazard to the subject. Investigators must report all deviations from the clinical protocol to MPO or its designated representatives as soon as possible. All deviations with the potential to affect subject safety, rights, or well-being must also be reported as required by the IRB/EC.

XVII. STUDY ETHICS

A. Ethics Committee Approval

It is the responsibility of the Investigator to obtain prospective approval of the clinical protocol, any clinical protocol amendments, Informed Consent document, and any other relevant documents from the IRB/EC. All correspondence with the IRB/EC will be retained in the Investigator Site File. Copies of IRB/EC approvals must be forwarded to MPO or its designated representative prior to enrolling subjects. The Investigator must immediately report to MPO or its designated representative if the IRB/EC withdraws its approval of the study for any reason.

B. Statements of Compliance

The study will be conducted in accordance with any applicable local, regional, or national subject privacy laws. Each site must have written approval from their respective IRB/EC prior to enrolling subjects.

C. Financial Disclosures

All Investigators must complete, sign and date the Financial Disclosure form prior to their participation in the study. Each Investigator must notify MPO or its designated representative if any relevant changes occur during the course of the study and for one

year following the completion of the study. Copies of the Financial Disclosure form for each Investigator will be maintained in MPO's investigational files.

XVIII. SPONSOR DISCONTINUATION CRITERIA

MPO reserves the right to terminate a non-performing site. Reasons for considering early termination or suspension of an individual site may include, but are not limited to:

- Site non-compliance with the clinical protocol or failure to comply with government or local regulations;
- Failure to submit data in a timely manner;
- Failure to comply with or act upon findings;
- Failure to take action to protect the rights and safety of human subjects;
- Failure to maintain pace to complete enrollment.

MPO reserves the right to discontinue the study at any time. After such a decision, the Investigator must also notify their respective EC of the discontinuation of the study. The Investigator must then contact all participating subjects to notify them of this decision and its impact on their follow-up per the guidance of the EC.

XIX. STUDY COMPLETION

A. Subject Completion

Individual subject participation will conclude once the subject has completed all required clinical visits and all outcome measurements required by the clinical protocol. The date of last follow-up, the date of study withdrawal, or date subject was determined to be lost to follow-up will be recorded.

B. Study Closeout Activities

The study will be considered complete once the last subject at the site has completed all clinical visits and all outcome measurements required by the clinical protocol. Additionally, the following activities must be completed at each site before the study is considered complete:

- All essential documents are complete and up to date
- Case report forms have been completed, entered into the electronic data capture (EDC) system, reviewed by the monitor, and all queries answered with related data updated, as applicable

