- Vomiting
- Hyperventilation

Adverse events associated with MRI include:

- Malfunctioning of heart pacemakers, defibrillation devices and cochlear implants
- Reaction to contrast media.

IX. STUDY OBJECTIVES

A. Primary Objective

The primary objective of the study is to determine the incidence of adverse local tissue reactions (ALTR) in each THA implanted with the WMT MoM THA System overall and for yearly cross-section intervals from 4-year to 8-year post implant.

B. Secondary Objective

The secondary objectives include:

- To determine whole blood and serum cobalt and chromium metal ion levels for subjects implanted with the WMT MoM THA System overall and for each defined cross-section interval
- To estimate baseline whole blood and serum and serum cobalt and chromium metal ion levels for subjects not implanted with any metal implants, and compare the cobalt and chromium metal ion levels between the implanted subjects and controls (Group-1 vs. Group-2 subjects).
- To compare functional outcomes, as assessed by HOOS score (Hip disability and Osteoarthritis Outcome Score), of subjects implanted with the WMT MoM THA System overall and for each defined cross-section interval in subjects with and without ALTR (Group-1 subjects).
- To compare cobalt and chromium metal ion levels in subjects with and without confirmed ALTR (Group-1 subjects).

X. STUDY DESIGN

A. Study Design

This is a cross-sectional, multi-center study to evaluate outcomes in subjects previously implanted for between 4 and 8 years prior to the study start date. A target of 5 sites, with up to 7 sites total, will participate in this study. Subjects will be identified from Investigator records. Collected data will be evaluated in aggregate and cross-sectioned by year of implantation according to the time that has elapsed between implantation.

B. Sample Size and Subject Cross-Sectioning

There will be two groups of subjects in this clinical study: **Group 1** will consist of subjects previously implanted with the WMT MoM THA System; **Group 2** (i.e., Control Group) will consist of control subjects not implanted with any other metallic devices (excluding dental implants).

The sample size for **Group 1** is 155 THAs that must have been implanted between 4 and 8 years prior to enrolling in this study. This sample size will allow for 35 THAs to be included at each 1-year interval between Years 5 and 8 and 15 THAs to be included in the Year 4 interval (Table 4).

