For each cross-section year, a sample size of 35 hips will give us a two-sided 95% confidence interval for the incidence rate of ALTR with a width no greater than 0.346. With the entire Group-1 cohort (n=155), the width of such a confidence interval will be no wider than 0.163.

The sample size for **Group 2** is 100 control subjects.

Subjects will be identified from Investigator records. Collected data will be evaluated in aggregate and cross-sectioned by year of implantation. Subjects will be cross-sectioned

by the time that has elapsed between implantation and the initial visit (e.g. 4 years, 5 years) using contiguous visit windows (number of years + 6 months).

As subject enrollment will be carried out in at least 5 sites, enrollment will begin with Group-1. Group-2 subjects will be matched by age and gender to Group-1 to achieve a more balanced distribution between the two groups. To minimize the potential of overenrollment, the study team will generate enrollment summaries and inform the sites if enrollment targets are reached for any given cross-sectioned year or for Group-2.

Table 4. Group 1 enrollment stratification based on time lapse from MoM THA implantation date to initial study visit.

Group 1	Year 4 + 6m	Year 5 + 6m	Year 6 + 6m	Year 7 + 6m	Year 8 + 6m
N (hips)	15	35	35	35	35

In comparing metal-ion levels between Group-1 and Group-2, we will have 90% power to detect a 0.65 standard-deviation unit difference as significant with 5% Type-1 error rate in each cross-sectioned year assuming that the ion levels in Group-1 and Group-2 will have similar variability. With the comparison of the entire Group-1 with Group-2, we can detect 0.4 standard-deviation unit difference as significant with 90% power and 5% Type-1 error rate.

Due to potentially enrolling both hips of a given patient, whenever data is collected for the patient, not for each hip, the data analysis for that particular study objective will be carried out at the patient level. If the data is collected for each hip for a given study objective, the data analysis will be carried out for each hip assuming that the hips are independent.

C. Primary Endpoint

The primary endpoint is an estimate of the incidence of ALTR in each THA implanted with the WMT MoM THA System overall and for each yearly defined cross-section interval.

D. Secondary Endpoints

The secondary endpoints include:

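### The interval width of 0.346 and the 90% power are claimed for every cross-section year, but Year 4 has 15 hips, where the width can reach 0.52 and power is about 64%

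*Protocol*

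**What the plan says.** All of the following is in Protocol Section X.B (Sample Size and Subject Cross-Sectioning).

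- **Allocation of Group 1.** The split is "35 THAs to be included at each 1-year interval between Years 5 and 8 and 15 THAs to be included in the Year 4 interval". The same numbers are in Table 4 and in the synopsis.
- **Precision.** "For each cross-section year, a sample size of 35 hips will give us a two-sided 95% confidence interval for the incidence rate of ALTR". The upper bound given for that width is 0.346. For the whole cohort: "With the entire Group-1 cohort (n=155), the width of such a confidence interval will be no wider than 0.163".
- **Power for metal ions, Group 1 against Group 2.** "we will have 90% power to detect a 0.65 standard-deviation unit difference as significant with 5% Type-1 error rate in each cross-sectioned year". This assumes similar variability in the two groups. The control group has 100 subjects.

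Neither the precision nor the power statement excludes Year 4, and no separate figure is given for 15 hips. The primary objective (Section IX.A) and primary endpoint (Section X.C) cover every yearly interval from Year 4 to Year 8.

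**The concern.** Two operating characteristics are attributed to all five cross-section years but appear to have been calculated for 35 hips, a size that only four of the years will have. The fifth has fewer than half as many.

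This is a postmarket surveillance study ordered by the FDA, with results reported by interval. If the section is taken at face value, a Year 4 ion comparison that fails to reach significance would be read as having a 10% chance of missing a 0.65 SD difference. If the power at 15 hips is much lower, that result could be mistaken for reassurance. Likewise, anyone planning around the Year 4 ALTR rate would expect a tighter interval than 15 hips can give.

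**Working it through.** **Inputs (all from Section X.B).** Hips per year: 15 in Year 4 and 35 in each of Years 5 to 8. Whole Group 1: 155. Controls: 100. Confidence level: 95%, two-sided. Type-1 error: 5%. Effect: 0.65 SD, with equal SDs. The sidedness of the ion test is not stated; two-sided is assumed, and one-sided is checked below.

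**1. Which interval gives the Protocol's widths?** The Clopper-Pearson limits for x events in n hips are

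- lower = Beta quantile 0.025 with parameters (x, n − x + 1)
- upper = Beta quantile 0.975 with parameters (x + 1, n − x)

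The maximum width is taken over all x.

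| n | Maximum exact width | Protocol |
|---|---|---|
| 35 | 0.3463 | 0.346 |
| 155 | 0.1625 | 0.163 |
| 15 | **0.5215** | 0.346, through the wording that covers each year |

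Both stated figures reproduce. Wald (0.331 and 0.157), Wilson (0.314 and 0.156) and Jeffreys (0.320 and 0.156) do not match them, so the exact interval is the method used. For Year 4 the ratio is 0.5215 / 0.3463 = 1.51.

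**2. Does the bound fail only near 50% incidence?** Exact intervals for 15 hips:

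| Events | 95% interval | Width |
|---|---|---|
| 0 | 0% to 21.8% | 0.218 |
| 1 | 0.2% to 31.9% | 0.318 |
| 2 | 1.7% to 40.5% | 0.388 |
| 3 | 4.3% to 48.1% | 0.438 |
| 7 | 21.3% to 73.4% | 0.5215 |

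The stated bound of 0.346 is already exceeded at 2 events, an observed rate of 13%.

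**3. Power of the ion comparison.** For a two-sample t-test, the noncentrality is 0.65 / √(1/n₁ + 1/100), with n₁ + 98 degrees of freedom.

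- n₁ = 35: 0.65 / √(0.02857 + 0.01) = 3.310; critical t = 1.978; power **90.8%**. This reproduces the stated 90%.
- n₁ = 15: 0.65 / √(0.06667 + 0.01) = 2.348; critical t = 1.981; power **64.3%** (65.1% by the normal approximation).
- n₁ = 15 with a one-sided 5% test: 75.4% (75.9% by the normal approximation), still well short of 90%.

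**4. Difference detectable with 90% power at n₁ = 15.** By the normal approximation: (1.960 + 1.282) × √(1/15 + 1/100) = 3.242 × 0.2769 = 0.898 SD. With the noncentral t it is **0.905 SD**. The corresponding value at n₁ = 35 is 0.641 SD.

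**The case against.** The arithmetic is not in dispute. The strongest points on the other side are these.

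- **The precision sentence names its own sample size.** It is true of any year with 35 hips, and the 15 for Year 4 is stated just before it and again in Table 4. This has some force: the fault there is loose wording that applies 35 to each year. It does not help the power sentence, which names no sample size and covers every year. That sentence is the plainer error.
- **The primary endpoint is an estimate, with no test or success threshold, and 95% intervals will be reported (Section XI).** The true width for Year 4 will therefore be visible in the results. This limits the harm for the ALTR rate. It does not make the planning statement correct.
- **The maximum width occurs only at 7 or 8 events of 15.** With 0 or 1 event the interval is within 0.346. That is right, and the Protocol gives no expected ALTR rate. But the Protocol states an upper bound, so maximum against maximum is the fair comparison, and the bound fails from 2 events on.
- **The secondary objectives do not explicitly ask for the Group 1 against Group 2 comparison by year.** The yearly comparison appears only in the power statement. This lowers its importance, but the power is still claimed.
- **No sample size, endpoint or analysis changes.** This is true, and it bears on how large the correction is, not on whether one is needed.

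**Conclusion.** The concern holds. The 0.346 width and the 90% power for 0.65 SD are correct for Years 5 to 8 and wrong for Year 4. There the maximum exact width is 0.5215, about 50% larger than stated. Power is about 64%, so the chance of missing a 0.65 SD difference is about 36% instead of 10%. The whole-cohort width of 0.163 is unaffected.

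The width rests on the exact interval, the method that reproduces the Protocol's own figures. The power rests on equal SDs, 100 controls, a two-sided 5% t-test and 15 separate patients in Year 4. Section X.B analyses patient-level data, such as ion levels, by patient. If any Year 4 patient contributes both hips, there are fewer than 15 patients and power is below 64%.

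**What to change.** In Section X.B, limit both statements to Years 5 to 8 and add Year 4. For example:

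> For Years 5 to 8 (35 hips each), the exact 95% confidence interval for ALTR incidence is at most about 0.346 wide, and there is 90% power to detect a 0.65 SD difference in ion levels from Group 2. For Year 4 (15 hips), the width is at most 0.522, power for 0.65 SD is about 64%, and the difference detectable with 90% power is about 0.91 SD. The power figures assume one enrolled hip per patient and a two-sided 5% test.

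The value 0.522 is 0.5215 rounded up, so that it remains a true bound. The sponsor may also wish to call the Year 4 ion comparison descriptive; that is a choice of emphasis and not part of the arithmetic correction.

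In the same edit, reconcile Section XIII.A (Enrollment Procedures), which tells sites to continue until 35 subjects are enrolled in each year window, with the 15 hips for Year 4 in Section X.B and Table 4.

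The cost is two sentences in Section X.B and one consistency edit in Section XIII.A. For Year 4, both the stated width and the stated power become less favourable. The enrolment targets in Table 4 and the planned analyses stay as they are. Section XV requires FDA and ethics committee approval for amendments, so the change could go with the next one.

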The product description, eight-digit product code, and lot number for each implanted component will be recorded for all subjects in **Group 1**. The number of acetabular screws used, if any, will also be recorded.

D. Whole Blood and Serum Metal Ion Levels (Both Groups 1 and 2)

Whole blood and serum cobalt and chromium metal ion levels will be collected in accordance with the Blood Draw Protocol for each subject **in both groups**. Bilateral subjects with both THAs enrolled will have a single blood draw and results will be used for both which will be entered into the database for both enrolled THAs.

E. HOOS Scores (Group 1 only)

HOOS Scores will be collected and recorded for each subject in **Group 1**. Bilateral subjects with both THAs enrolled will be asked to complete a separate HOOS Score for each THA.

F. MARS MRI (Group 1 only)

MARS MRI will be collected in accordance with the Imaging Protocol for each subject in **Group 1**. Bilateral subjects with both THAs enrolled may have a single MARS MRI, if sufficient for both THAs. Each side will be reviewed separately.

G. Adverse Events (both Groups 1 and 2)

Adverse events will be recorded in accordance with the Adverse Event Section below.

H. Revisions (Group 1 only)

Any enrolled THAs revised prior to the closure of the last site will have their WMT MoM THA System components explanted and analyzed in accordance with the Retrieval Analysis Protocol. Additionally, periprosthetic tissue and synovial fluid samples will be collected, as available, and analyzed in accordance with the Retrieval Analysis Protocol.

Please note: although a revision procedure is not considered a study-related activity, MPO will analyze and report the findings of the retrieval analyses resulting from revisions during the study period.

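### The 90% power claimed for 0.4 SD in the full Group 1 versus Group 2 ion comparison is at most about 87%, and 155 hips is only an upper bound on the number of patients

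*Protocol*

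**What the plan says.** Protocol section X.B sets Group 1 at 155 THAs and Group 2 at 100 control subjects. Table 4 in that section counts hips: 15 in Year 4 and 35 in each of Years 5 to 8.

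Two power statements follow for the ion comparison, made "assuming that the ion levels in Group-1 and Group-2 will have similar variability". The first gives 90% power for 0.65 SD in each cross-sectioned year. The second covers the whole cohort: "we can detect 0.4 standard-deviation unit difference as significant with 90% power and 5% Type-1 error rate".

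The next paragraph of X.B sets the unit of analysis. Where data are collected per patient and not per hip, "the data analysis for that particular study objective will be carried out at the patient level". Section XIII.D settles which kind of data ions are: "Bilateral subjects with both THAs enrolled will have a single blood draw". Sections XII.A and XIII.A allow both hips of a patient to be enrolled, and section X.D plans ion summaries split by one or both hips enrolled. No expected number of bilateral patients is given.

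**The concern.** The overall power figure does not follow from the sample sizes printed beside it, even on the most favourable count. The only sample size given for Group 1 is in hips, while the protocol's own rule makes the comparison one of patients. The two counts agree only if nobody enrols both hips.

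The ion comparison between implanted and control subjects is a named secondary objective. Section V reports that the regulator's orders centre on ion concentrations. A reader of a null or borderline result would use the stated power to judge how much it means, so the figure should be one that the design has.

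**Working it through.** **Inputs, all from Protocol X.B.** Group 1 at most 155 patients (155 hips, none shared); Group 2 100; difference 0.4 SD; equal SDs; alpha 5%. Sidedness is not stated for the ion test, so it is inferred in step 1.

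**Formulas.** SE = sqrt(1/n1 + 1/n2) in SD units. Normal approximation: power = Φ(d/SE − 1.960) and detectable difference = (1.960 + 1.282) × SE. The t figures use the noncentral t distribution with n1 + n2 − 2 degrees of freedom and noncentrality d/SE.

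**Step 1. Reproduce the companion figure (35 vs 100, 0.65 SD).** SE = sqrt(1/35 + 1/100) = 0.1964 and d/SE = 3.310. Two-sided power is Φ(3.310 − 1.960) = 91.1% (t: 90.8%), which matches the stated 90%. A one-sided 5% test gives 95.2% (t: 95.0%), which does not. The method is therefore confirmed, and the paragraph is consistent with two-sided testing.

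**Step 2. Apply it to the overall claim (155 vs 100, 0.4 SD).** SE = sqrt(1/155 + 1/100) = 0.1283 and d/SE = 3.119.
- Two-sided power: Φ(3.119 − 1.960) = 87.7% (t: 87.4%).
- Difference detectable with 90% power: 3.242 × 0.1283 = 0.416 SD (t: 0.417).
- One-sided power: 93.0% (t: 92.9%), which does not reproduce 90% either.
- Group 1 patients needed for 90% power at 0.4 SD with 100 controls: 192 (t: 196).

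**Step 3. Convert hips to patients.** If a fraction b of Group 1 patients enrol both hips, patients = 155/(1 + b). The values of b above zero are assumptions; results are by t, two-sided.

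| b | Patients | Power at 0.4 SD | Detectable at 90% |
|---|---|---|---|
| 0 | 155 | 87.4% | 0.417 SD |
| 10% | 141 | 86.2% | 0.43 SD |
| 20% | 129 | 84.8% | 0.434 SD |
| 30% | 119 | 83.5% | 0.442 SD |

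**Step 4. Yearly intervals at 0.65 SD (t, two-sided, 100 controls).**

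| Distinct patients | Power |
|---|---|
| 35 | 90.8% |
| 34 | 90.2% |
| 33 | 89.5% |
| 15 (Year 4, at most) | 64% |

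For Year 4, SE = sqrt(1/15 + 1/100) = 0.277, and 90% power is reached only at about 0.91 SD (normal approximation 0.90).

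**The case against.** **Rounding.** The detectable difference of 0.417 SD may simply have been printed as 0.4, which would make the certain gap 0.017 SD or 2.6 power points. This largely stands, and it keeps the point small. But the rounding goes in the favourable direction, whereas the companion figure was rounded the safe way (0.641 to 0.65). It also cannot explain the use of hips for a patient-level comparison.

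**Sidedness.** A one-sided test would exceed 90%. The protocol does not exclude one in words, but the companion figure reproduces only two-sided, and the one sidedness stated in the section is two-sided: "a sample size of 35 hips will give us a two-sided 95% confidence interval for the incidence rate of ALTR".

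**Size of the bilateral loss.** A reader might infer that true power is in the low eighties. The protocol does not support that, because it gives no bilateral share. Only the direction is established.

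**Yearly claims.** A reader might also infer that bilateral enrolment undermines 0.65 SD in every year. It need not: section XIII.A notes that a patient's two hips may fall in different intervals, and then neither interval loses a distinct patient. The claim survives at 34 patients and is only just short at 33. Year 4 is different, because its planned size is 15.

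**Enrolment text.** Section XIII.A speaks of 35 subjects in each year window, which would give 5 × 35 = 175. Even 175 patients give 88.9% (t), and X.B, Table 4 and the synopsis all fix 155.

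**Consequence.** The planned patient-level analysis is sound, section XI plans 95% confidence intervals for the endpoints, and the primary ALTR estimate is per hip and unaffected. All of this stands.

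**Conclusion.** The stated 90% power for 0.4 SD is not delivered. At the maximum of 155 patients against 100 controls it is about 87%, and 90% is reached at about 0.42 SD. This rests on equal SDs, which the protocol assumes, and on two-sided 5% testing, which its companion figure implies. Each bilateral patient lowers the power from that ceiling by an amount the protocol does not allow anyone to fix; the 10% to 30% rows are illustrations.

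The 0.65 SD claim is right for Years 5 to 8 with 34 or 35 distinct patients per interval and wrong for Year 4, where power is about 64%.

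This is a modest correction to planning statements for a secondary objective. It does not show an invalid analysis, a fault in the primary precision statement, or a need to enrol more subjects.

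**What to change.** Restate the ion power paragraph of section X.B in patients and name the sidedness. Suggested content:

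- *Overall:* with at most 155 Group 1 patients and 100 controls, power is at most about 87% for 0.4 SD, or 90% for about 0.42 SD (two-sided 5%), and lower if bilateral subjects are enrolled.
- *Years 5 to 8:* 90% power for 0.65 SD, given about 34 to 35 distinct patients in the interval.
- *Year 4:* with at most 15 patients against 100 controls, about 64% power for 0.65 SD; 90% only at about 0.91 SD.

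Do not write a patient range based on a guessed bilateral share into the protocol. If the sponsor has an expected share from site records, it can be added with its source.

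The cost is a few sentences and a slightly less favourable figure. Enrolment, visits and analysis stay as they are.
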